Study Design	Pragmatic comparative open study comparing oral and transdermal pubertal induction
Study Participants	Girls with Turner syndrome aged ≥11.0 years requiring pubertal induction
Planned Size of Sample	84 patients in each treatment arm – transdermal and oral = 168 total
Follow up duration	Follow up will be for at least the duration of induction: 3 years in most girls, 3 ½ years in especially short girls, and 2 years in the case of older girls receiving a shortened induction protocol. However, where possible, follow up will be continued until final adult height is achieved (usually around 16 years)
Planned Study Period	Eight years (including set-up and recruitment)
Research Question/Aim(s)	Is transdermal induction of puberty in girls with Turner syndrome superior to oral induction in terms of:
	Height gain during the 3-year induction period? This is the primary outcome measure

	Adult height, cardiovascular health (systolic blood pressure, aortic root dilatation), uterine health (uterine shape and size), bone health (bone mineral density), patient satisfaction and acceptability (adherence to each regime). These are secondary outcome measures
Brief synopsis of study	Most girls with Turner syndrome (TS) require pubertal induction with estrogen, followed by long term replacement. However, no adequately powered prospective studies comparing transdermal with oral 17β - estradiol administration exist. This reflects the difficulty of securing funding to study a rare condition with relatively low morbidity/mortality when competing against conditions such as cancer and vascular disease.
	The TS Working Group of the European Society for Paediatric Endocrinology (ESPE) has reached a consensus for two 3-year pubertal inductions regimens – one transdermal and one oral. A shorter regimen for the minority of girls presenting aged >14 years has also been devised.
	Prerequisites include suitable 17β-estradiol tablets and matrix patches to allow the delivery of incremental doses based on body weight.
	We wish to carry out an international prospective cohort study with single centre analysis in which clinicians and families are invited to choose either of the agreed regimens, usually starting at 11 years. We hypothesise that pubertal induction with transdermal estradiol will result in better outcomes for some key parameters.
	Data analysis will include assessment of the demographics and drop-out rates of patients choosing either oral or transdermal preparations; and appropriate analysis of outcomes including pubertal height gain, final height, adherence/acceptability, uterine health (assessed with pelvic ultrasound) cardiovascular health (blood pressure measurement and cardiac ultrasound, and bone health (assessed with DXA).
	This proposed model of prospective data collection according to internationally agreed protocols aims to break the current impasse in obtaining evidence-based management for TS.
	(See Donaldson et al [21])

FUNDING AND SUPPORT IN KIND

FUNDER(S)	FINANCIAL AND NON		
(Names and contact details of ALL	FINANCIALSUPPORT GIVEN		
organisations providing funding and/or	See above. Funding has been obtained to		
support in kind for this study)	curate the proposed database in the context		
	of the international disorders of sex		
	development (i-DSD), managed by Professor		

[name], Child Health Section, University of Glasgow School of Medicine.
Funding will be required to support a data manager, responsible for coordinating the running of the study both in the UK and mainland Europe

ROLE OF STUDY SPONSOR AND FUNDER

The sponsors (in the UK, University of Glasgow or NHS Greater Glasgow and Clyde) will be asked to support this pragmatic study. There is no perceived risk inherent in this proposed study since girls with TS requiring estrogen for pubertal induction, together with their families, are being asked to choose one of two approved regimens which are already in use in current medical practice.

ROLES AND RESPONSIBILITIES OF STUDY MANAGEMENT COMMITEES/GROUPS & INDIVIDUALS

The Turner Syndrome Working Group of the European Society for Paediatric Endocrinology has 38 members of which 7 are members of the TSWG Steering Group – these members are responsible for study management. TSWG had requested pharmacy support from Alder Hey Children's Hospital.

The Turner Syndrome Support Society in the UK is aware of and supportive of the study (see Donaldson et al [21])

PROTOCOL CONTRIBUTORS

1 BACKGROUND

Turner syndrome (TS) is a condition in which there is loss of the second sex chromosome (either X or Y) and/or abnormality of the second X chromosome in at least one major cell line in a phenotypic female. Features include short stature and primary ovarian insufficiency, accompanied by typical phenotypic traits and a variety of associated cardiac and renal malformations in a minority [1,2].

TS carries a significant morbidity and mortality [3,4]. Long-term health consequences for cardiovascular disease and osteoporosis are particularly important. Problems such as aortic dissection (arising particularly in girls with previously repaired aortic coarctation or bicuspid aortic valve), hypertension, atheroma and increased risk of metabolic syndrome [5,6,7,8,9,] give rise to a marked increase in mortality rate (standardised mortality ratio 3) and a life expectancy 13 years less than the general population, a finding similar to patients with diabetes. However, since TS has a relatively low prevalence, affecting about 1 in 2000 live female births [1], there is little awareness of the condition and its implications.

Appropriate, physiological sex steroid replacement is essential in the optimal management of patients with TS from puberty through to the age of normal menopause. Estrogen induction of puberty is usually required in TS, a retrospective Italian study showing that spontaneous onset of periods (menarche) occurred in only 84 of 522 (16.1%) patients [10]. Puberty is a highly important process both physically and psychologically. Over 50% bone mineral accrual occurs during puberty & the early post-pubertal years [11]. Moreover timely pubertal induction is important for self-esteem, psychosexual development and quality of life.

The European Society of Human Reproduction and Embryology (ESHRE) has developed clinical practice guidelines for the management of women with primary ovarian insufficiency (POI) [12]. Clinical practice guidelines for the care of girls and women with TS were published after the International Turner Syndrome Meeting in Cincinnati [13]. Matthews and colleagues from the United Kingdom (UK) have described a consensus from the British Society for Paediatric Endocrinology and Diabetes on hormone supplementation for pubertal induction in girls with POI [14]. Christin-Maître published a review on the use of hormone replacement in females with endocrine disorders [15]. However, the Cincinnati guidelines do not cover pubertal induction in depth, and the other papers mentioned do not deal specifically with TS.

While transdermal estrogen treatment has theoretical advantages over oral treatment and has been used in Sweden for decades (16), the evidence for any superiority is lacking. Matthews et al write, "There is a real paucity of carefully constructed, randomised controlled clinical trials in girls undergoing induction of puberty. The evidence base is derived mainly from expert experience, a small number of observational studies and very few controlled trials on small study populations. In addition, studies of treatment acceptability and patient adherence are lacking" [14]. Thus, while transdermal delivery of physiological 17β -estradiol estrogen may be superior to oral ethinylestradiol in terms of cardiac, bone and uterine health in POI [17,18,19], adequately powered studies are needed to address these as well as other elements such as growth during pubertal induction, adherence and acceptability [20].

The Turner Syndrome Working Group (TSWG) of the European Society for Paediatric Endocrinology (ESPE) proposes a large prospective international pragmatic study in which girls and families are invited to choose either an oral or transdermal protocol, both of which have been agreed by TSWG and comparing outcomes with each regimen. This proposal has been peer-reviewed and published in the journal Hormone Research in Paediatrics [21]. The paper emphasizes that the proposal is not a randomised clinical trial which would be logistically impractical, considering the patient numbers required for adequate power would demand international recruitment, making such a study unrealistically costly to fund. However, rigorous planning to collect and compare prospective data on girls treated according to defined, disciplined protocols and with agreement on primary & secondary outcomes together with expert statistical analysis of the outcomes, will allow valid conclusions to be drawn in an area where current evidence is very poor.

Of note, this pragmatic proposal lies within the scope of what has been described by Torgerson as a "Patient Preference Trial" [22].

Transdermal vs oral 17β-estradiol protocol Version 1.0 July 12th 2020

2 RATIONALE

Aim: To compare the outcome and acceptability of transdermal and oral pubertal induction in TS, using the natural estrogen 17β -estradiol in both regimens.

3 RESEARCH QUESTION/AIM(S)

Research question: Is transdermal 17β-estradiol induction superior to oral induction in terms of key parameters including pubertal height gain and adult height, cardiac (e.g. blood pressure), uterine and bone health, and in acceptability?

Study hypothesis: Induction of puberty using transdermal 17β -E2 will result in better outcomes for some key parameters.

3.1 Objectives

The study objectives are to compare outcomes between the oral and transdermal TSWG regimens.

3.2 Outcomes

The primary outcome measure is height gain in cm during the pubertal induction period, since this can be accurately determined in the context of an international framework. Secondary outcome measures include final adult height, systolic blood pressure, aortic root diameter, uterine size and shape, bone mineral density, adherence and dropout rate.

Table 1 Outcome measures to be analysed at the end of pubertal induction in girls with Turner syndrome using either an oral (see Tables 2a and 2b) or transdermal (see Tables 3a and 3b) 17- β estradiol regimen approved by the Turner Syndrome Working Group of ESPE.

Induction period is normally 3 years (plus 6 months for very short girls), exceptionally 2 years for girls presenting late (e.g. >14 years), minimum follow up is during induction period but where possible, follow up is to final adult height.

Primary outcome measure

Pubertal height gain, i.e. increase in height in centimetres during the (usually) 3-year pubertal induction period

Secondary outcome measures

- Final adult height in centimetres & population-specific SDS
- Change in population-specific height SDS between start and end of pubertal induction
- Breast development (clinical assessment)
 - Tanner B4-5 reached
 - Satisfactory breast shape (ie not tubular, no overdevelopment of areolae) according to attending clinician (graded as satisfactory or unsatisfactory)
- Cardiovascular health
 - Systolic & diastolic blood pressure at the end of induction (lowest of three readings or mean values if recorded by ambulatory 24-hour blood pressure monitoring
 - Change in aortic root diameter and aortic size index between start and completion of induction
- Patient satisfaction; adherence/compliance with treatment
 - Percentage drop-outs from either regimen
 - Average of good, reasonable and poor rating with adherence during pubertal induction (3 years ± X months)
 - Patient satisfaction with shape and size of breast (scoring 1-5 where 5=best)
 - Patient satisfaction with mode of administration (scoring 1-5 where 5=best)
- Uterine health and sex hormone profile at the end of induction
 - Uterine length and volume, endometrial thickness
 - Uterine shape and fundo-cervical ratio
 - LH and FSH
 - Serum 17-β estradiol

- Skeletal age and bone health
 - Change in bone age/chronological age per year
 - Change in size-adjusted whole body lumbar spine and hip bone mineral areal density (BMAD) (z-score) before and after induction
- Metabolic profile

Number of patients in each group in whom all parameters are normal at the end of induction for:

- Liver function
- Cholesterol, triglycerides, low and high density lipoproteins, apoprotein A1, B and A1:B ratio
- Fasting glucose and insulin (HOMA)

4 STUDY DESIGN and METHODS of DATA COLLECTION AND DATA ANALYIS

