Table 2b Two-year oral 17β -estradiol regimen for pubertal induction in girls presenting late (e.g. >14 years) and judged by clinician and family to require a shorter induction period. Year 3 corresponds to post-induction dose. The dose is calculated according to body weight at the beginning of each year and given before sleep each night.

Year (months)	Dose of estradiol [microgram/kg/day]
1 (0-6)	5
1 (7-12)	7.5
2 (13-18)	10
2 (19-24)	15
3 (25-36)	20 [†]

Transdermal vs oral 17β-estradiol protocol Version 1.0 July 12th 2020

During the fourth year of maintenance treatment, estradiol dose will vary between 1-4 mg daily, depending on patient sensitivity, most patients requiring at least 2 mg daily.

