4.5 Data collection before and during pubertal induction

Table 4 shows the recommended information to be collected before, during and at the end of pubertal induction, and until adult height, i.e. height velocity < 2 cm/year.

TABLE 4 Recommended measurements before, during and at the end of pubertal induction with either transdermal or oral 17-β
estradiol grouped according to priority – essential and desirable.

Variable	Before induction (± 6 months)		End of Years 1 & 2	End of Year 3	Comment	
ESSENTIAL	(2 o montho)	visito				
Karyotype	X				From time of diagnosis	
Auxology Height (cm)	x	x	x	х		
Weight (kg)	X	Х	X	Х	 Previous growth data will be requested, to enable calculation of a) height velocity, using 12 (±1) month interval, during previous year; and GH responsiveness – derived from height/weight status one year prior to, at the start of, and one year after starting GH. 	
Height velocity (cm/yr)	X		X	Х		
Measured parental heights (where available)	X					
Breast and pubic hair stage (1-5)	X	Х	X	Х		
Systolic & diastolic blood pressure (mm Hg)	Х	Х	Х	Х	Lowest of three consecutive readings using Dinamap V100 or similar device	
Adherence to treatment		X	Х	Х	Scored according to estrogen doses missed per month as good (≤ 2) moderate (≤ 4) and poor (> 4)	
Adverse events/illness		Х	Х	Х	All adverse events (e.g. injury, intercurrent infection) irrespective of relevance to growth and puberty	
FSH, LH	X			Х		
Free T4 and TSH	Х			Х		
Liver function	Х		Х	Х		
HbA1c	Х			Х		
Concurrent treatment	Х	Х	Х	Х	GH, L-T4, Oxandrolone	
DESIRABLE	1					
Final adult height					Measurement once height velocity < 2cm/year	
Bone age	Х		Х	Х	Assessed using 'BoneXpert', where available	
Sitting height	X	X	Х	Х		
Echocardiography	X			Х	Including measurement of aortic size index	
Pelvic ultrasound	Х		X	Х	Uterine length, shape and volume, endometrial thickness	
DXA BMC	Х			Х	Hip and lumbar spine z-score Total body BMD	
Fasting lipid profile	Х			Х	Cholesterol, triglycerides, low and high-density lipoproteins	
Coagulation studies	X			Х		
Serum estradiol	X			Х	Beginning of Year 4 (see Table 2)	
Serum IGF-I	X		Х	Х	Keep +1.5 -2.5 SD of reference range	
24h continuous ambulatory blood pressure	X			Х		
Fasting blood glucose and insulin	Х			Х		

Abbreviations

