4.6 Data analysis

When the target number of patients has been enrolled (see below), and a sufficient number (84 in each arm) have completed the full 3-year induction, the following analyses between the transdermal and oral groups will be conducted:

- Demographics of patients choosing oral or transdermal estradiol preparations, differences at baseline
- Numbers of patients in each treatment arm, their centres and countries
- Adherence to each of the treatment arms including % of dropouts
- Propensity score matching to reduce bias due to confounding factors e.g. 45,X karyotype, midparental height, height at the beginning of pubertal induction, duration of prior GH treatment, GH responsiveness and treatment or not with oxandrolone.
- Use of Directed Acyclic Graphs to establish the minimally sufficient set of confounders for each outcome parameter, entering these into multivariable regression models

The minority of girls undergoing a 2-year induction will be analysed separately and their outcomes compared with the majority of girls undergoing the full three-year induction

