5 STUDY SETTING

This is a multicentre, international study which includes the UK. The study setting will be in endocrine clinics and centres within the UK, other European countries, and beyond. Treatment administration and data collection will be carried out as indicated above. A single European centre will receive

Transdermal vs oral 17β -estradiol protocol Version 1.0 July 12^{th} 2020

anonymised data from study participants at enrolment and at the end of each year of the pubertal induction regimen chosen.

Participating centres and countries are likely to have at least some ESPE members. Centres must have facilities for recording the essential data required for good management in TS (see section 5.5).

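### Table 4 closes at End of Year 3, so girls on the 2-year induction have no consistent end-of-induction time for several secondary outcomes

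*Protocol*

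**What the plan says.** Table 1 (section 3.2) is captioned "Outcome measures to be analysed at the end of pubertal induction in girls with Turner syndrome". Its note on duration reads "Induction period is normally 3 years (plus 6 months for very short girls), exceptionally 2 years for girls presenting late". The metabolic profile at the end of that table (liver function, lipids, fasting glucose and insulin) is also tied to the end of induction.

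Table 4 (section 4.5) is captioned "Recommended measurements before, during and at the end of pubertal induction with either transdermal or oral". It has a column for values before induction, one for visits, one headed "End of Years 1 & 2", and one closing column, End of Year 3. No footnote adapts the closing column to a shorter or longer schedule.

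The caption of Table 2b (section 4.2.1) says of the 2-year oral schedule that "Year 3 corresponds to post-induction dose". Table 3b says the same of the patch. The synopsis gives minimum follow-up as the length of induction, that is "2 years in the case of older girls receiving a shortened induction protocol".

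Section 4.6 plans this use of the data: "The minority of girls undergoing a 2-year induction will be analysed separately and their outcomes compared with the majority of girls". Section 5 has centres send data "at enrolment and at the end of each year of the pubertal induction regimen chosen".

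**The concern.** The outcome definition moves with the induction schedule, but the measurement schedule does not. The two agree only for the 3-year girls. For a 2-year girl, the closing set of tests falls in a year that the protocol itself calls post-induction, and at a time when she may have left follow-up.

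This cannot be left to an analysis plan. A blood sample or scan not taken at month 24 cannot be recovered later. At stake is the section 4.6 comparison of 2-year with 3-year girls on several secondary outcomes. A difference there could come from when the measurement was taken and on what dose, rather than from the length of induction.

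**Working it through.** **1. Month 36 against the end of each schedule**, counted from the start of treatment:

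| Schedule | Induction ends | 36 minus end |
|---|---|---|
| 2-year (Tables 2b, 3b) | month 24 | +12 months |
| 3-year (Tables 2a, 3a) | month 36 | 0 |
| 3.5-year (notes to Tables 2a, 3a) | month 42 | −6 months, only if Year 3 is a calendar year |

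**2. What Table 4 does capture at month 24.** The column for Years 1 and 2 marks height, weight, height velocity, breast stage, blood pressure, adherence, adverse events, liver function, concurrent treatment, bone age, sitting height, pelvic ultrasound and IGF-I: 13 rows. Section 4.5 also asks for height, blood pressure, pubertal stage and adherence at each visit. The primary outcome therefore has its month-24 value.

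**3. What it does not.** Ten rows are marked before induction and at End of Year 3 only. They divide as 3 + 4 + 3 = 10:

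- Three are Table 1 outcomes with no other scheduled time: lipids, fasting glucose/insulin and 24-hour ambulatory blood pressure.
- Four are Table 1 outcomes whose timing in the text conflicts with the table. Section 4.5 puts echocardiography and DXA at the end of induction, and FSH/LH and estradiol every year. Estradiol has further timings: the Table 4 comment says the beginning of Year 4, while the note to Table 3b says early in Year 3.
- Three are not Table 1 outcomes: free T4/TSH, HbA1c and coagulation. No outcome definition is contradicted for these.

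**4. Would a month-36 value reach the database?** Minimum follow-up for these girls ends at month 24. Section 5 transfers data at the end of each year of the chosen regimen, which for a 2-year induction most naturally means months 12 and 24. A girl who starts after age 14 is past 17 at month 36 (14 + 3), while the synopsis expects adult height at around 16. A month-36 value is therefore far from assured.

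**5. How different the dosing is at month 36.** This describes the exposure contrast only; it is not an effect on any outcome.

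- Oral: the last induction step is 15 and the post-induction dose 20 microgram/kg/day, so 20/15 = 1.33. The protocol adds that most patients need at least 2 mg daily. At 50 kg (the weight at which 20 microgram/kg gives the protocol's approximate 1 mg), 15 × 50 = 750 microgram = 0.75 mg, and 2/0.75 = 2.7.
- Patch, below 50 kg: the full piece (16.7 microgram/24 h) is worn overnight and half of it (8.35) by day. Assuming 11 hours overnight, the average is (16.7 × 11 + 8.35 × 13)/24 = 12.2. With 10 to 12 hours it is 11.8 to 12.5. Against 50 to 75 microgram/24 h, 50/12.2 = 4.1 and 75/12.2 = 6.2.

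**6. The sample size is untouched.** The plan's figure reproduces: 21/(2.5/3.5)² = 41.2, rounded up to 42 and doubled to 84 per arm. Section 6.2 excludes the shortened-induction girls from that target.

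**The case against.** The strongest reply is that this is only a label. The caption of Table 4 and the opening of section 4.5 both refer to the end of induction, and section 3.2 requires lipids and glucose/insulin at that point, so a sensible centre would move the closing tests to month 24. That is a fair guess at the intention. But an outcome definition is not a sampling schedule, and the only schedule given for those rows places them a year late. That section 3.2 requires them at the end of induction makes the conflict sharper. For blood pressure the reply has more force: Table 1 accepts a clinic reading, and one exists at month 24. What is lost is the ambulatory value, so a 3-year girl may contribute an ambulatory mean where a 2-year girl can contribute only a clinic reading.

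It is also true that seven of the ten rows are classed as desirable and left to the clinician, so some missing data are already accepted. That limits the weight of the point. It does not excuse a schedule that adds missing or mistimed values in one group of a planned comparison.

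Two stronger readings are tempting, and the protocol does not support them:

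- A reader might infer that 2-year girls have no end-of-induction data at all. The month-24 marks and the every-visit rule show otherwise, including for the primary outcome.
- A reader might infer that 3.5-year girls are assessed six months early and that, because the extra six months sits at different points of the oral and patch schedules, a false route effect follows. This needs Year 3 to mean calendar year. Table 2a inserts the oral extension between Years 2 and 3, and section 5 speaks of years of the chosen regimen. Regimen year is the more natural reading, and on it the closing assessment is at month 42. Height is also taken at every visit.

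**Conclusion.** The point holds in a limited form. Table 1 and Table 4 disagree on when closing outcomes are measured in 2-year girls, by 12 months. Seven Table 4 rows that feed Table 1 outcomes are involved: three with no other scheduled time, and four where table and text conflict. Followed as written, these values are missing or taken under post-induction dosing, and the 2-year against 3-year comparison in section 4.6 is distorted for those outcomes.

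The main route comparison in 3-year girls is not affected, because 2-year girls are analysed separately and are outside the 84 per arm. For 3.5-year girls the only fault is an undefined term: month 42 if Year means regimen year, month 36 if it means calendar year. The protocol does not state how many girls will follow the 2-year or 3.5-year schedule, so the number affected cannot be given. The dose ratios rest on the stated assumptions of 50 kg, 2 mg and 10 to 12 hours of overnight wear; the conclusion does not depend on them.

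**What to change.** - In Table 4, rename the last column: End of induction (month 24, 36 or 42, according to the girl's induction schedule). State that Table 1 end-of-induction values come from this column.
- State that Year means regimen year, and say in which year the extra six months is counted, since the notes to Tables 2a and 3a place it differently.
- Reconcile the Table 4 estradiol comment with the 2-year tables and with the annual measurement in section 4.5.
- In section 5, name the end of induction as a data transfer point.

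No month-36 measurement should be required of all girls, as it would exceed the minimum follow-up of the 2-year girls.

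The cost is a column heading and a few sentences. No tests are added, because the closing set is simply taken at month 24 in 2-year girls. The 3.5-year girls need at most one further data transfer.

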Induction of puberty will be from 11 years. Specific age of beginning induction, and duration of induction are at the discretion of the clinician in consultation with the family. Initiation of treatment in eligible patients should normally begin at between 11-12 years, consistent with the Cincinnati and UK guidelines [13,14]. Pubertal induction should normally be carried out over a 3-year period. However, a later induction age will be necessary in girls presenting >12 years. Also, a faster induction period (e.g. 2 years) should be considered in girls who are older (e.g. >14 years) at the time of starting induction due to late diagnosis.

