4.2.1 Oral induction

The agreed oral three-year induction protocol, derived from the Dutch regimen of Bannink et al [23], together with a final (fourth) year, of maintenance treatment is shown in Table 2a. A 2-year protocol for older girls (e.g. aged >14 years) in whom a shorter induction period is desired by the clinician and family, is given in Table 2b

Dose is based on body weight and is recalculated at the beginning of each year.

 $17-\beta$ estradiol will be given in its micronized (e.g. Estrace) or hemihyrate (e.g. Cetura) form using 0.5 mg tablets which can be halved by the family.

Alternatives such as esters - $17-\beta$ estradiol valerate (e.g. Climaval and Zumenon) and hemihyrate preparations (e.g. Elleste solo and Estrofem) are acceptable but only available as 1 mg tablets so that participating centres would therefore need their pharmacy to prepare a suitable dose from a 1 mg tablet.

Girls receiving <0.25 mg daily with any preparation would also need their medication prepared by the pharmacist. Girls receiving <0.25 mg daily with any preparation will require their pharmacy to prepare the correct dose in capsule form, as currently practiced in The Netherlands using Cetura. (Documentation from Amalia Children's Hospital, Radboud University Medical Center, Nijmegen, available on request). In patients requiring ≥0.25 mg daily the dose will be rounded to the nearest 0.25 mg. Evening administration is recommended, to mirror the transdermal regimen.

Table 2a Three-year oral 17β -estradiol regimen for pubertal induction and, in italics, a suggested first post-induction year [21]. The dose is calculated according to body weight at the beginning of each year and given before sleep each night.

Year (months)	Dose of estradiol [microgram/kg/day]
1 (0-12)	5
2 (13-24)*	7.5
3 (25-30)	10
3 (31-36)	15
4 (37-48)**	20†

*Girls in whom low final height is anticipated or who are markedly short at the start of induction (defined as ≤3 standard deviations below the population mean) may be offered a slower induction by receiving an extra 6 months of 7.5 microgram/kg/day between Year 2 and Year 3. **Morning serum estradiol sample is recommended at the beginning of Year 4.

[†]This post-induction dose equates to about 1 mg daily. However, the dose required will vary between 1 and 4 mg daily, depending on patient sensitivity, most patients requiring at least 2 mg daily.

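### The primary outcome is raw height gain over an induction of discretionary length (3 or 3.5 years), so an arm with more extended inductions would gain height from longer observation alone

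*Protocol*

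**What the plan says.** Section 3.2, Table 1, gives the primary outcome as "increase in height in centimetres during the (usually) 3-year pubertal induction period". The same table describes the period: "Induction period is normally 3 years (plus 6 months for very short girls), exceptionally 2 years for girls presenting late". The synopsis words the outcome more narrowly: "Height gain during the 3-year induction period? This is the primary outcome measure".

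Section 4.2 states: "Specific age of beginning induction, and duration of induction are at the discretion of the clinician in consultation with the family". The optional extra six months is set out in footnotes that differ by route. Under Table 2a (oral), girls with a low anticipated final height, or who are markedly short at the start, "may be offered a slower induction by receiving an extra 6 months of 7.5 microgram/kg/day between Year 2 and Year 3". Under Table 3a (transdermal), only low anticipated final height is named, and the extra six months is at the Year 1 dose.

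Section 4.6 analyses 2-year girls separately, with "their outcomes compared with the majority of girls undergoing the full three-year induction". Section 6.2 excludes only the shortened induction from the target of 84 per arm, and its planning value, 12.2 (3.5) cm, is a gain over three years. Neither section says how 3.5-year girls enter the analysis. Starting height and midparental height are among the example confounders in section 4.6; length of induction is not.

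**The concern.** A gain in centimetres depends on how long the girl is watched. Under Table 1 as worded, one girl's gain may cover 36 months and another's 42, and both count as the same outcome. In a randomised comparison with one common extension rule, this would mainly add noise. Here the family chooses the route, the extension is optional, and the two footnotes describe eligibility for it differently. Unequal shares of extended inductions are therefore plausible. If they occur, part of any difference between routes would reflect observation time rather than growth response.

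A second, lesser matter is the planned comparison of 2-year with 3-year girls. For raw height gain it sets two years of growth against three, in girls who also start at different ages.

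**Working it through.** **Inputs.** From section 6.2: mean gain 12.2 cm over three years, SD 3.5 cm, target difference 2.5 cm, 90% power, 5% level, 84 per arm. From sections 4.4 and 4.5: 2 cm/year, the Protocol's threshold for near-adult height, used here as a low value for growth velocity. The share of extended girls in each arm is not given, so it is assumed.

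**The plan's own figure.** f = 2.5/3.5 = 0.714, and 21/f² = 41.2, which rounds up to 42 per arm. With f rounded to 0.71 it is 41.7, again 42. A two-sided two-sample calculation also gives 42. Power is 90.5% at 42 per arm and 99.6% at 84. The sample size is sound for a three-year gain.

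**Value of six more months.**
- At the mean velocity: 12.2/3 = 4.07 cm/year, and 0.5 × 4.07 = 2.03 cm (81% of 2.5 cm).
- At 2 cm/year: 0.5 × 2 = 1.0 cm.

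**Bias between arms** = (difference in share extended) × (growth in six months). The false-positive rate assumes no true effect and uses a normal approximation with standard error 3.5 × √(2/84) = 0.540 cm.

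| Difference in share (assumed) | Bias at 1.0 cm | False-positive rate | Bias at 2.03 cm | False-positive rate |
|---|---|---|---|---|
| 0 points | 0 | 5% | 0 | 5% |
| 10 points | 0.10 cm | 5.4% | 0.20 cm | 6.6% |
| 20 points | 0.20 cm | 6.6% | 0.41 cm | 11.7% |
| 30 points | 0.30 cm | 8.6% | 0.61 cm | 20.4% |

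For the 20-point row at 2.03 cm: 0.41/0.540 = 0.75 standard errors, so the two tail areas beyond ±1.96 sum to 11.7%. That bias is 16% of the target difference; at 1.0 cm it is 8%.

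If the bias ran against a true 2.5 cm difference, power at 84 per arm would fall from 99.6% to 98.9% (1.0 cm) or 97.2% (2.03 cm) for 20 points. The damage is therefore mainly to the estimate and the error rate, not to power.

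**2-year versus 3-year girls.** At equal velocity, 2 × 4.07 = 8.13 cm against 12.2 cm. The gap of 4.07 cm comes from time alone and is 1.6 times the target difference.

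**The case against.** The strongest reply is that gain over induction as actually delivered is a legitimate pragmatic outcome, and that a 36-month cut compares extended girls who are still in induction with girls who have finished. That is a real cost: it exchanges unequal time for unequal treatment stage. It does not rescue the present wording, because the synopsis and the planning value both refer to three years.

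It can also be said that confounding is already handled. Extension is tied to shortness, starting height and midparental height are named for matching, and causal diagrams are planned for each outcome. This helps in part. Anticipated final height and clinician discretion also decide who is extended, so matching on starting height cannot be relied on to equalise the shares. Final adult height does not depend on the induction window, but it is a secondary outcome.

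The size rests on assumed shares. Very unequal shares, such as half of one arm extended, fit poorly with the synopsis, which expects three years for most girls. The 2.03 cm figure applies an average velocity to girls with a poor height prognosis and may be too high. Both cautions stand, which is why a range is given.

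A reader might also infer more than the text supports:
- That pooling of 3.5-year girls is stated. It is only implied, because nothing but the 2-year schedule is set aside.
- That Table 4 has no visit for the end of an extended induction. In both regimens the extra six months comes before the Year 3 dose step, so the End of Year 3 column can be read as that visit.
- That extension is decided in response to growth on treatment. This is possible, but the footnotes do not say so.
- That the 2-year girls distort the oral–transdermal result. They are analysed separately and do not enter it.

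**Conclusion.** The point holds in a bounded form. The primary outcome has no common time point, its wording differs between the synopsis and Table 1, and the text implies that 36-month and 42-month gains are pooled. Bias between routes arises only if the share of extended inductions differs between arms. Nothing in the Protocol keeps the shares equal, and the design makes a difference plausible. For an assumed 20-point difference the bias is about 0.2 to 0.4 cm (8–16% of 2.5 cm), with a two-sided false-positive rate of about 6.6–11.7% at 84 per arm. With equal shares it is zero. The sample size is not in error.

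The 2-year versus 3-year comparison of raw gain is confounded by time, by about 4.1 cm at equal velocity. This carries less weight because it lies outside the main comparison, and the objection does not apply to adult height.

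**What to change.** Define the primary outcome in Table 1 as height at 36 months after first dose minus height at first dose, for every girl on the 3- or 3.5-year schedule, whatever dose step she has reached. State a visit window, because End of Year 3 in Table 4 could mean 36 months or the end of the Year 3 dose step at 42 months. For extended girls, name the 36-month height in the central data transfer described in section 5. Keep gain to the end of induction as a secondary outcome, and report induction length by arm.

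In section 4.6, compare routes within the 2-year group. For height gain, either make the 2-year versus 3-year comparison at 24 months adjusted for age at start, or drop it.

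Reconcile the statements on induction length and extension in the synopsis, Table 1, section 4.2 and the footnotes to the oral and transdermal tables. No view is taken here on which rule is right.

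The cost is wording. Height is already essential at each visit, with visits every 3 to 6 months. No treatment changes, and the 42 and 84 per arm stand because the planning value is itself a three-year gain. The one downside is that extended girls have not finished induction at 36 months; the secondary outcome covers their remaining growth.
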